4.5.1.2 Treatment Administration

The first day of dosing is considered Day 1.

Investigational product (MEDI8897 or placebo) will be supplied by an unblinded investigational product manager. Blinding will be performed at the site level to ensure that MEDI8897 and placebo are indistinguishable in appearance and are not labeled to reveal treatment identity.

Investigational product (MEDI8897 or placebo) should be administered in the anterolateral aspect of the thigh according to standard practice procedures for IM injections.

4.5.1.3 Monitoring of Dose Administration

Subjects will be monitored before and after investigational product administration through assessment of vital signs (temperature, blood pressure, heart rate, and respiratory rate). All vital signs should be obtained within 60 minutes prior to dosing, at 30 minutes (\pm 5 minutes) and at 60 minutes (\pm 5 minutes) post dose.

As with any antibody, allergic reactions to dose administration are possible. Therefore, appropriate drugs and medical equipment to treat acute anaphylactic reactions must be immediately available, and study personnel must be trained to recognize and treat anaphylaxis.

4.5.1.4 Reporting Product Complaints

Any defects with the investigational product must be reported *immediately* to the MedImmune Product Complaint Department by the site with further notification to the site

monitor. All defects will be communicated to MedImmune and investigated further with the Product Complaint Department. During the investigation of the product complaint, all investigational product must be stored at labeled conditions unless otherwise instructed.

MedImmune contact information for reporting product complaints:

Email: [contact]

[REDACTED]

4.5.2 Additional Study Medications

No other study medications are specified for use in this clinical protocol.

4.5.3 Labeling

Labels for the investigational product will be prepared in accordance with GMP and local regulatory guidelines. Label text will be translated into local languages, as required.

4.5.4 Storage

Store investigational product at 2°C to 8°C.

4.5.5 Treatment Compliance

Investigational product is administered by study site personnel who will monitor compliance.

4.5.6 Accountability

The investigator's or site's designated investigational product manager is required to maintain accurate investigational product accountability records. Upon completion of the study, copies of investigational product accountability records will be returned to MedImmune. All unused investigational product will be returned to a MedImmune-authorized depot or disposed of upon authorization by MedImmune.

4.6 Treatment Assignment and Blinding

4.6.1 Methods for Assigning Treatment Groups

An IWRS will be used for randomization to a treatment group and assignment of blinded investigational product kit numbers. A subject is considered randomized into the study when the investigator notifies the IWRS that the subject meets eligibility criteria and the IWRS provides the assignment of blinded investigational product kit numbers to the subject.

Subjects will be randomized at a 2:1 ratio to receive a ■ mg IM dose of MEDI8897 (N = 1,000) or placebo (N = 500). Randomization will be stratified by temperate zones in the northern and southern hemisphere and by subject age at the time of randomization (ie, ≤ 3 months, $> 3 - \leq 6$ months, > 6 months). Enrollment of infants > 6 months of age will be limited to approximately 500.

The procedure for using IWRS is as follows:

- The investigator or designee contacts the IWRS and provides the SID number and subject's baseline characteristic(s) used to verify that it is the same subject
- Placebo (provided by site) or a vial from a MEDI8897 kit will be assigned to the subject
- Confirmation of this information is sent to the unblinded investigational product manager who prepares the investigational product to be dispensed to the subject per the response system and records the appropriate information in the investigational product accountability log

Investigational product (MEDI8897 or placebo) must be administered the same day the investigational product is assigned. Total in-use storage time from needle puncture of the investigational product vial to administration should not exceed 4 hours at room temperature. If storage time exceeds these limits, a new vial should be used. If there is a delay in the administration of investigational product such that it will not be administered within the specified timeframe, the unblinded investigational product monitor must be notified immediately.

4.6.2 Methods for Ensuring Blinding

This is a double-blind study in which sites are using commercially available saline as the placebo. MEDI8897 and placebo are visually indistinguishable once in syringes. Neither the subject/legal representative nor any of the investigator or site staff who are involved in the treatment or clinical evaluation of the subjects will be aware of the treatment received (International Council for Harmonisation [ICH] E9). In the event that treatment allocation for a subject becomes known to the investigator or other blinded study staff involved in the management of study subjects, the sponsor must be notified *immediately*. If the treatment

allocation for a subject needs to be known to treat an individual subject for an AE, the investigator must notify the sponsor *immediately*. The site will maintain a written plan detailing which staff members are blinded/unblinded and the process of investigational product administration used to maintain the blind.

4.6.3 Methods for Unblinding

4.6.3.1 Unblinding in the Event of a Medical Emergency

In the event of a medical emergency, the investigator may unblind an individual subject's investigational product allocation. Instructions for unblinding an individual subject's investigational product allocation are contained in the IWRS manual. In general, unblinding should only occur if management of the medical emergency would be different based on the subject having received investigational product. In the majority of cases, the management of a medical emergency would be the same whether or not investigational product was received by the subject. If this was the case, the investigational product allocation should not be unblinded.

MedImmune retains the right to unblind the treatment allocation for SAEs that are unexpected and are suspected to be causally related to an investigational product and that potentially require expedited reporting to regulatory authorities.

4.6.3.2 Unblinding for Primary Analysis Purposes

The primary analysis will be conducted when all randomized subjects have completed the Day 151 visit and will include all efficacy data for all randomized subjects. All efficacy and safety data collected up to the Day 151 visit and available safety data beyond Day 151 at the time of that data cut-off date will be included in the primary analysis. Efficacy and safety for MEDI8897 will be evaluated in this unblinded analysis.

Sponsor personnel will be unblinded at this primary analysis. Study site personnel and the subjects' parent(s)/legal guardian will remain blinded to the treatment assignment of individual subjects until the last subject completes the study and the final database is locked.

4.7 Restrictions During the Study and Concomitant Treatment(s)

The Investigator must be informed as soon as possible about any medication taken from the time of screening until the end of the clinical phase of the study (final study visit). Any concomitant medication(s), including herbal preparations, taken during the study will be recorded in the electronic case report form (eCRF).

4.7.1 Permitted Concomitant Medications

Investigators may prescribe concomitant medications or treatments deemed necessary to provide adequate supportive care including routine vitamins and iron.

4.7.2 Prohibited Concomitant Medications

Use of concomitant medications including over-the-counter medications (except for routine vitamins and iron), herbal supplements, etc from Day 1 through Day 15 post dose is discouraged. Subjects' legal representatives must be instructed not to administer any medications, including over-the-counter products, without first consulting with the investigator.

4.8 Statistical Evaluation

4.8.1 General Considerations

There are two planned analyses for this study: the primary analysis and the final analysis. The primary analysis will be conducted after all randomized subjects have completed the Day 151 visit, and the final analysis will be conducted when all subjects have completed the last visit of the study (Day 361).

Tabular summaries will be presented by treatment group. Categorical data will be summarized by the number and percentage of subjects in each category. Continuous variables will be summarized by descriptive statistics. Additional details of statistical analyses will be described in the statistical analysis plan.

The intent-to-treat (ITT) Population is defined as all subjects who are randomized. Subjects will be included in the treatment group corresponding to their randomized treatment. All analyses, with the exception of safety, will be performed on the ITT Population.

The As-treated Population will include all subjects who are randomized into the study and who receive any amount of investigational product. Subjects will be included in the treatment group corresponding to the treatment actually received. All safety analyses will be performed on the As-treated Population.

4.8.2 Sample Size and Power Calculations

The sample size of 1,500 is necessary based on advice from the US FDA requesting that 1,000 preterm infants be exposed to MEDI8897 in this Phase 2b study. This sample size has approximately 99% power to detect 70% relative risk reduction, assuming a placebo group medically attended RSV LRTI incidence of 8%. Power calculations are based on Poisson

regression model with robust variance (Zou, 2004) comparing MEDI8897 [REDACTED] mg versus placebo, with 2-sided significance level of $\alpha = 0.05$.

- The 70% relative risk reduction assumption is based on a placebo-controlled study in Native American infants in which there was 87% relative reduction in the incidence of RSV hospitalization (11.3% placebo; 1.5% motavizumab; $p < 0.001$) and 71% relative reduction in the incidence of outpatient RSV LRTI (10.0% placebo; 2.9% motavizumab; $p < 0.001$) in infants who received motavizumab prophylaxis (O'Brien et al, 2015)

In order to evaluate risk, a sample size of 1,000 subjects exposed to MEDI8897 will provide a 90% probability of observing at least one AE if the true event rate is 0.2%; if no AEs are observed, this study provides 95% confidence that the true event rate is $< 0.3\%$.

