4.8.3 Efficacy Analysis

The primary analysis will be conducted after all randomized subjects have completed the Day 151 visit. At the time of this primary analysis, approximately half of all subjects enrolled (722 subjects) will have completed the Day 361 visit. The remaining 731 subjects will have completed approximately 8 months of the study.

The primary and secondary efficacy hypotheses will be assessed in the primary analysis by a hierarchical order. That is, the secondary hypothesis will be tested at a significance level of 0.05 only if the treatment effect on the primary efficacy endpoint is demonstrated at the significance level of 2-sided 0.05. With that, the overall Type I error is controlled at 0.05. Therefore, no further multiplicity adjustment is necessary.

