2.4 Sample Size

The sample size of 1,500 subjects is necessary based on advice from the United States Food and Drug Administration US FDA requesting that 1,000 preterm infants be exposed to MEDI8897 in this Phase 2b study. This sample size has approximately > 99% power to detect 70% relative-risk reduction, assuming a placebo group medically attended RSV LRTI incidence of 8%. Power calculations are based on a Poisson regression model with robust variance (Zou, 2004) comparing MEDI8897 50 mg versus placebo, with 2-sided, $\alpha = 0.05$.

- The 70% relative-risk reduction assumption is based on a placebo-controlled study in Native American infants in which there was 87% relative reduction in the incidence of RSV hospitalization (11.3% placebo; 1.5% motavizumab; $p < 0.001$) and 71% relative reduction in the incidence of outpatient RSV LRTI (10.0% placebo; 2.9% motavizumab; $p < 0.001$) in infants who received motavizumab prophylaxis (O'Brien et al, 2015)

In order to evaluate risk, a sample size of 1,000 subjects exposed to MEDI8897 will provide a 90% probability of observing at least one AE if the true event rate is 0.2%; if no AEs are observed, this study provides 95% confidence that the true event rate is < 0.3%.

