3 STATISTICAL METHODS

3.1 General Considerations

Summary statistics will be tabulated by treatment group. Categorical data will be summarized by the number and percentage of subjects in each category. Continuous variables will be summarized by mean, median, standard deviation, minimum, and maximum. In general, unless stated otherwise, baseline will be defined as the last non-missing value prior to dosing.

There are two planned analyses for this study: the Primary Analysis and the Final Analysis. The Primary Analysis will be conducted after all randomized subjects have completed the Day 151 visit. At the time of this primary analysis, approximately half of all subjects enrolled (722 subjects) will have completed the Day 361 visit. The remaining 731 subjects will have completed approximately 8 months of the study. MEDI8897’s efficacy will be evaluated in the Primary Analysis as intended by the study design. In addition, all available PK, ADA, and safety data will be analyzed. The final analysis will be conducted when all subjects have completed the last visit of the study.

Data analyses will be conducted using the SAS® System Version 9.3 or higher (SAS Institute Inc., Cary, NC) in a SAS GRID environment.

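### With 1,000 infants exposed, the chance of seeing at least one adverse event at a 0.2% rate is 86.5%, not 90%; separately, the 722 and 731 subject counts need reconciling with 1,500

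*Protocol*

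**What the plan says.** Protocol 4.8.2 justifies the sample size by a regulator's request for 1,000 preterm infants exposed to MEDI8897. It then describes what that exposure can show about safety. For "a sample size of 1,000 subjects exposed to MEDI8897" it claims "a 90% probability of observing at least one AE if the true event rate is 0.2" percent. It adds that, with zero events, the true rate can be put below 0.3% with 95% confidence. The synopsis carries the same two claims. SAP version 5, section 2.4, repeats both: exposure of 1,000 "will provide a 90% probability of observing at least one AE if the true event rate is 0.2" percent and, with no events, "this study provides 95% confidence that the true event rate is < 0.3" percent.

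Both documents plan 1,500 infants randomized 2:1, which is 1,000 on MEDI8897 and 500 on placebo. Protocol 4.8.3 also describes where subjects will stand at the primary analysis: "approximately half of all subjects enrolled (722 subjects) will have completed the Day 361 visit. The remaining 731 subjects" will have about 8 months in the study. SAP 3.1 gives the same two counts.

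**The concern.** The 90% figure and the 0.2% rate do not belong together at 1,000 exposed. The sentence is the plan's only quantitative statement of what the safety database can detect or exclude, and exposure is the stated reason for the size of the trial. As printed, it implies a 10% chance of missing an event type with a true rate of 0.2%. The actual chance is 13.5%, about a third higher.

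The second issue is one of consistency. If the 731 are the rest of all enrolled subjects, enrolment was 722 + 731 = 1,453, and it is unclear how that fits with the unchanged 1,500 and 1,000. The safety figures depend on the number exposed, which is not stated anywhere apart from the planned 1,000.

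**Working it through.** **Inputs.** Exposed n = 1,000, true rate p = 0.2%, claimed probability 90%, and claimed zero-event bound of 0.3% at 95% confidence (Protocol 4.8.2; SAP 2.4). Subject counts 722 and 731 (Protocol 4.8.3; SAP 3.1). Allocation 2:1 of 1,500 (Protocol 4.1.1).

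**1. Probability of at least one event, 1 - (1 - p)^n.**
- Binomial: 1 - 0.998^1000 = 0.8649, or 86.5%.
- Poisson: 1 - exp(-0.002 × 1000) = 1 - exp(-2) = 0.8647, or 86.5%.
- Other denominators do not give 90% either: n = 1,500 gives 95.0% and n = 1,453 gives 94.5%.

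The stated 90% is therefore not reproduced. The gap is 3.5 percentage points.

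**2. What 90% would require.**
- Rate at n = 1,000: 1 - 0.1^(1/1000) = 0.00230, or 0.23%.
- Number exposed at 0.2%: ln(0.1)/ln(0.998) = 1,150.1, so 1,151 infants.

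**3. Zero-event bound, one-sided 95%, 1 - 0.05^(1/n).**
- n = 1,000: 0.00299, or 0.299%. The rule of three gives 3/1000 = 0.300%. The plan's figure is reproduced.
- Smallest n with a bound below 0.3%: ln(0.05)/ln(0.997) = 997.1, so 998. The margin at 1,000 is two infants.

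**4. The subject counts.**
- 722 + 731 = 1,453. Neither document prints this sum, or the number exposed.
- If 1,500 were enrolled and 722 had completed Day 361, the rest would be 1,500 - 722 = 778, not 731. The difference is 47 subjects, which is 47/1500 = 3.1%.
- 722 is about half of either total: 722/1453 = 49.7% and 722/1500 = 48.1%.

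**5. Range under two readings** (assuming an exact 2:1 split and every randomized infant dosed).

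| Reading | Exposed | P(at least one event) at 0.2% | Zero-event 95% bound | Confidence that rate < 0.3% |
|---|---|---|---|---|
| 1,500 randomized | 1,000 | 86.5% | 0.299% | 95.04% |
| 1,453 randomized | about 969 (1453 × 2/3 = 968.7) | 85.6% | 0.309% | 94.6% |

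**6. Efficacy power** (8% against 2.4%, two-sided 0.05, pooled two-proportion formula): 99.6% at 1,000:500 and 99.5% at 968:484. The plan's statement of about 99% or more holds either way.

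**The case against.** The best defence of the 90% is rounding. At 1,000 exposed, a rate of 0.23% gives 90.0%, and 0.23% prints as 0.2% to one decimal. That may well be how the figure arose. It does not rescue the sentence: a reader takes 0.2% at face value, and the pair as printed is wrong. It does make the correction simple. It is also fair to say that the 90% did not set the sample size (the exposure request did) and that no test, suspension criterion or analysis uses it.

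A reader might go further and infer that the 0.3% bound also fails and that the 1,000-exposed target was missed, since 1,453 split 2:1 is about 969. The documents do not support that. The bound is explicitly tied to 1,000 exposed and is right on that basis. The 722 and 731 are described by follow-up reached, so they could leave out subjects who dropped out of a larger enrolment. This is a single-dose trial, and Protocol 4.8.1 puts everyone who received any investigational product in the As-treated Population, so an infant lost after dosing still counts as exposed. Protocol 4.1.7 also allows replacement of early discontinuers, and a dosed infant who is replaced remains exposed. The number exposed therefore cannot be derived from these counts.

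What remains is the natural reading of the sentence in Protocol 4.8.3, in which the 731 are the rest of all enrolled. On that reading the counts conflict with 1,500, and neither document explains the difference.

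**Conclusion.** The 90% is wrong as written: with the plan's own inputs the probability is 86.5%. This rests only on independent events at a common rate, and the binomial and Poisson forms agree. The 0.3% bound is correct for 1,000 exposed and should stay, although it holds only from 998 exposed upwards.

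The 722 and 731 counts justify a request for reconciliation and nothing stronger. If 1,453 is total enrolment, split exactly 2:1 with all infants dosed, the figures become about 85.6% and 0.31%. If 1,500 were randomized and dosed, they are 86.5% and 0.299%. Even the less favourable case is a small shift, 94.6% confidence instead of 95%. Efficacy power and the analyses are unaffected, so this is a descriptive correction.

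**What to change.** In the Protocol synopsis, Protocol 4.8.2 and SAP 2.4, replace the claim with either 86.5% (or 86%) at a true rate of 0.2%, or 90% at a true rate of 0.23%, both for 1,000 exposed. Keep the 0.3% zero-event bound and note that it needs at least 998 exposed.

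In Protocol 4.8.3 and SAP 3.1, say whether 722 + 731 is all randomized subjects or only those still in follow-up, explain how it relates to 1,500, 1,000 and 500, and state the number who received MEDI8897. If that number proves to be about 969, restate the safety figures for it: about 85.6% at 0.2%, 90% at about 0.24%, and a bound of 0.31%.

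The cost is wording only. The detection figure becomes slightly less favourable, and no analysis, test or sample size changes.

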4.8.3 Efficacy Analysis

The primary analysis will be conducted after all randomized subjects have completed the Day 151 visit. At the time of this primary analysis, approximately half of all subjects enrolled (722 subjects) will have completed the Day 361 visit. The remaining 731 subjects will have completed approximately 8 months of the study.

The primary and secondary efficacy hypotheses will be assessed in the primary analysis by a hierarchical order. That is, the secondary hypothesis will be tested at a significance level of 0.05 only if the treatment effect on the primary efficacy endpoint is demonstrated at the significance level of 2-sided 0.05. With that, the overall Type I error is controlled at 0.05. Therefore, no further multiplicity adjustment is necessary.

4.8.3.1 Primary Efficacy Analysis

The incidence of RSV LRTI (inpatient and outpatient) during 5 months of the RSV season will be based on RSV test results (performed centrally via RT-PCR) and objective clinical LRTI criteria and will be summarized by treatment group. For subjects with multiple medically attended RSV LRTI events, only the first occurrence will be used in the primary analysis.

The primary efficacy analysis of the primary endpoint will be conducted with the ITT Population. LRTI caused by RSV that occurs prior to discontinuation from participation in the study will contribute to the primary efficacy analysis. For subjects who do not have an RSV LRTI prior to discontinuation from participation, their event status will be imputed assuming the observed placebo RSV LRTI rate. This will be implemented by imputations based on repeated simulations and will be described in the Statistical Analysis Plan. A Poisson regression model with robust variance (Zou, 2004) will be used as the primary

efficacy analysis model to compare the incidence of medically attended RSV LRTI between MEDI8897 and placebo, including treatment group, age at the time of randomization (ie, ≤ 3 months, $> 3 - \leq 6$ months, > 6 months) and dichotomous temperate (northern and southern) hemispheres as covariates. In addition, the 2-sided p-value and corresponding 2-sided 95.1% CI on the relative risk will be provided from the model. Relative risk reduction is defined as $(1 - P_n/P_s)$ where P_n is the incidence of RSV LRTI during 5 months of the RSV season in the MEDI8897 group and P_s is the incidence of RSV LRTI during 5 months of the RSV season in the placebo group generated from the model. Statistical significance will be achieved if the 2-sided p-value is ≤ 0.05 .

4.8.3.2 Additional Analyses of the Primary Endpoint

A CMH (Cochran-Mantel-Haenszel) approach stratified by hemisphere and age at the time of randomization (ie, ≤ 3 months, $> 3 - \leq 6$ months, > 6 months) will be used to compare the incidence of RSV LRTI during 5 months of the RSV season between treatment groups as a sensitivity analysis for the primary endpoint. In addition, a time-to-event analysis assessing time to first RSV LRTI may be performed as a supplementary analysis.

An analysis may also include all RSV positive LRTI endpoints, using results from either the central lab or local lab.

Different approaches to handle missing data (ie, early discontinuation and no RSV LRTI prior to discontinuation) may be considered for sensitivity analyses. Additional analyses or subgroup summaries may be performed to adjust duration of efficacy follow-up and/or other possible confounding factors. These analyses will be described in the Statistical Analysis Plan.

